### Inclusion Criteria

1. Age 18-75 (to maximize participation)
2. Can currently be using prescription opiates
3. Has current chronic back pain (> 3 months)
4. Able to read and understand questionnaires and informed consent.

Protocol version: 3.0

Protocol date: 07/14/2020

5. Is not at elevated risk of seizure (i.e., does not have a history of seizures, is not currently prescribed medications known to lower seizure threshold)
6. Does not have metal objects in the head/neck.
7. Does not have a history of traumatic brain injury, including a head injury that resulted in hospitalization, loss of consciousness for more than 10 minutes, or having ever been informed that they have an epidural, subdural, or subarachnoid hemorrhage.
8. Does not have a history of claustrophobia leading to significant clinical anxiety symptoms.

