**MRI scanning:** The MRI scanning session will last 30 minutes and will contain: 1) a high resolution anatomical image (T1-weighted MPAGE (TR 1.9 sec, TE 2.26 ms, 2x GRAPPA, 1 mm isotropic)), 2) resting state functional connectivity (TA 7 minutes, voxel size: 2.5 x 2.5 x 2.5, TR = 2.6 s, TE = 25 ms, flip angle = 60°, FOV = 224 mm x 224 mm, matrix size = 64 x 64), For each of the above strategies (Active rTMS or Active Sham) we will explore a series of SubAims designed to quantify the effects of rTMS on subjective pain, quantitative sensory testing, and brain reactivity to pain.

**SubAim 1- Evaluating Pain using Clinical Assessments and Quantitative Sensory Testing (QST):** Using the Medoc ATS pressure algometer (Medoc Ltd Advanced Medical Systems, Ramat Yishai, Israel), 3 primary outputs will be compiled for each individual via the method of limits (54): sensory threshold, pain threshold, tolerance threshold. The algometer has a rubber tip that will be pressed into the right forearm for the procedure. Participants will indicate when they first detect the pressure change (sensory threshold), when it becomes painful (pain threshold), and when they can no longer tolerate the stimuli (tolerance threshold). When participants indicate tolerance, the operator will release the algometer. QST will be performed at the following timepoints: for the first TMS visit, the QST will be administered prior to the first TMS session and immediately following the second TMS session; for the remainder of the TMS visits and follow-up visits, QST will be performed prior to the first TMS session at each visit. The acute changes for TMS visit 1 will give one measure for acute pain changes pre/post TMS. **Pain**

**Questionnaire.** In order to evaluate current levels of pain, we will ask participants to rate their current level of pain and discomfort (scale, 0 through 10), each time the participant comes in (Table 1). On days where the individual receives rTMS, they will fill out this assessment between each TMS session. **Pain and Craving Questionnaire:** In addition to the Pain Questionnaire above, participants will also rate their urge to use a pain reliever (Scale 0 – 10) and the amount they would be willing to pay for a pain reliever (in US Dollars). This questionnaire will be used at the same time during each intervention visit as the Pain Questionnaire (Table 2).

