### **Outcome Measure(s)**

- A. Quantitative Sensory Testing.** The QST pain assessment produces 3 output variables: sensory threshold, pain threshold, tolerance threshold (all expressed in kiloPascals). The hypothesis will be tested using a within-subject repeated measures design (time x treatment) wherein time is the repeated variable and Real or Placebo TMS is the grouping variable. Given that the purpose of this pilot study is to develop effect sizes for a subsequent R01, we will derive least-squares means effect sizes of this strategy on these thresholds. Secondary analyses will evaluate the relationship between QST levels and the neural response to pain, as well as the relationship between QST values and evoked cortical responses. Integrating these measures together will provide a more complete picture of how cortical activity is able to modulate the pain response.
- B. Questionnaires and Evaluations.** The Opiate Pain inventory produces 4 output variables of interest: level of discomfort, level of pain, urge to use opiates, amount willing to pay for an opiate. The hypotheses for the Aims will be tested using a within-subject repeated measures design (time x treatment) wherein time is the repeated variable and Real or Placebo TMS is the grouping variable. Given that the purpose of this pilot study is to develop effect sizes for a subsequent R01, we will derive least-squares means effect sizes of our research strategy on these 4 variables, to determine the unique contributions of this intervention.

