- C. Neuroimaging Data (Aim 2):** Immediately following acquisition, functional structural data will be uploaded to a secure data server and converted to NIfTI format. All preprocessing and analyses will be performed using Statistical Parametric Mapping 12 (SPM12) in Matlab 2013 (Mathworks). Functional data will be corrected for magnetic field inhomogeneity and realigned (rigid-body, minimizing least squares differences) to the first image in the time series (Realign: Estimate and Unwarp). Non-linear deformations required for standard space normalization will be derived from each participant's anatomical image via a unified segmentation approach (Segment). After the mean realigned and unwarped functional image is coregistered to the skull stripped anatomical image (Coreg: Estimate) forward deformations (subject space to MNI standard space) will be applied (Normalise: Write). Finally, the data will be smoothed by an 8 mm full width half maximum Gaussian smoothing kernel (Smooth). Within-subject and between-group modeling. Data will be analyzed at the subject level using multivariate pattern analysis (Wager et al 2013 “An fMRI-Based Neurologic Signature of Physical Pain” new England Journal of Medicine). The six motion parameters (translations and rotations) will be included in the design matrices as covariates to account for non-task signal.

Resting State Connectivity will be measured to compare MRI scan 1 to scan 2 – immediately after the treatment. MRI scan 3 will also be compared to these scans to see if there is a sustainable reduction in pain activity between these networks. Additionally factor analysis will be used to investigate the durability of the effects of each strategy on functional connectivity in each of the 3 Core networks (SN, ECN, DMN) using factor analysis longitudinally. **Covariates:** As an exploratory analysis we will also quantify the impact of several covariates which have previously been documented to affect the brain response to pain and pain thresholds (sex, Becks Depression Inventory score, length of time using chronic opiates). Although all participants will have taken their daily dose of opiates, which has a stable pharmacokinetic profile, we will also consider time since last dose.

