**Expected (and alternative) Outcomes:**

- A. **Quantitative Pain Testing.** Based on our pilot data, we expect an interaction between treatment (Real DPFC or MC TMS vs. Sham) and time (Before vs. After rTMS) on the painfulness QST measure but no effect on sensory or tolerance levels. Alternative outcomes: It is possible that individuals will experience a small level of acute pain relief from their normal regimen of medication. We will be collecting information on opiate dose and timing at each visit to be used as potential covariates. Further, there is the possibility that pain tolerance will rise, possibly also reflecting improvements in executive function.
- B. **Qualitative Pain Assessment.** We expect reductions in pain and discomfort when comparing active vs sham. However, based on prior data in opiate dependent individuals, we expect the effect size of DPFC rTMS in to improve measures of Control but not measures of mood, whereas MC will have a larger effect on mood.
- C. **Neuroimaging.** At baseline we expect that there will be elevated activations in the Pain Network in individuals with chronic pain. Following sham stimulation, we do not anticipate a significant reduction of this response. Based on prior studies by our group in non-opiate dependent individuals, following LTP-like stimulation of the DPFC, we expect a significant amplification of the DPFC (% BOLD signal change), and a reduction of the Pain Network (dACC, anterior insula) reflecting the increased influence of executive processes.

Alternative outcomes: Though pilot data suggest that a single treatment will acutely reduce self-reported pain, it is possible that the neural circuits in opiate dependent individuals do not have the same ‘plasticity potential’ as in controls. If we fail to replicate prior work showing DPFC activation, this could reflect executive deficits (58), suggesting that the MC TMS will be more efficacious.

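### Two questionnaire outcomes are named as opiate craving although the form asks about any pain reliever, and the covariate text wrongly takes every participant to be on opiates

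*Combined protocol and SAP*

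**What the plan says.** **Population.** The Inclusion Criteria allow opiate use without requiring it: "Can currently be using prescription opiates". Subjects selection criteria and Interventions and Interactions say the same. The Innovation paragraph presents the mix of users and non-users as a deliberate feature of the design.

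**What is collected.** SubAim 1 in General Methods describes a Pain Questionnaire (current pain and discomfort, each from 0 to 10) and a Pain and Craving Questionnaire, on which "participants will also rate their urge to use a pain reliever" (0 to 10) and state how many dollars they would pay for one.

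**What is analysed.** Outcome Measure(s), part B, takes four variables from an Opiate Pain inventory: discomfort, pain, and then "urge to use opiates, amount willing to pay for an opiate". Part B uses them to test the hypotheses of the Aims by time and treatment, and derives least-squares means effect sizes for a later R01.

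**Covariates.** Outcome Measure(s), part C, introduces its list this way: "As an exploratory analysis we will also quantify the impact of several covariates". The list includes "length of time using chronic opiates". It then says "Although all participants will have taken their daily dose of opiates" and adds "we will also consider time since last dose". Part A of Expected (and alternative) Outcomes says, for the sensory testing, "We will be collecting information on opiate dose and timing at each visit to be used as potential covariates".

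**The concern.** Both problems look like text from a design in which everyone was an opiate user, left in place for a mixed sample.

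The outcome label matters more. Demand for a pain reliever and demand for an opiate are different constructs. A participant who has never taken an opiate can answer the form with an over-the-counter product in mind, and so can a current user. The protocol's own safety text treats over-the-counter remedies as pain relief, for headache after stimulation. The Background and Objectives sections stress the need to reduce reliance on opiates, so an effect size labelled as opiate craving invites a conclusion that the data cannot carry, and the label would pass into the planning of the next trial.

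The covariate sentence matters less. It states something untrue of the enrolled population, and it leaves no rule for entering opiate covariates for people who take no opiates.

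**Working it through.** No arithmetic settles this point; it rests on setting the sections side by side.

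**Step 1. Are the analysed and the collected items the same?**

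| Part B output | Item in SubAim 1 | Same construct? |
|---|---|---|
| Discomfort | Discomfort, 0 to 10 | Yes |
| Pain | Pain, 0 to 10 | Yes |
| Urge, for opiates | Urge, for a pain reliever, 0 to 10 | No |
| Payment, for an opiate | Payment, for a pain reliever, in dollars | No |

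The four outputs pair one for one with the four items. The name Opiate Pain inventory appears nowhere else, and the Assessments paragraph lists a pain craving form but no opiate inventory. Treating them as one set of items is therefore a strong inference, but still an inference.

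**Step 2. How much of part B is affected?** Two of four outputs. Pain and discomfort carry the same meaning in both places.

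**Step 3. Would analysing users only rescue the label?** No. The item does not name opiates, so a user's answer is also about any pain reliever. The sample mix makes the problem more visible, but the wording of the item causes it.

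**Step 4. Which opiate covariates fail for a non-user?**

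| Covariate | Value for a non-user | Status in the plan |
|---|---|---|
| Length of opiate use | 0 is natural | Exploratory (part C) |
| Opiate dose | 0 is natural | Potential (Expected Outcomes, part A) |
| Time since last dose, or dose timing | None | To be considered (part C); potential (Expected Outcomes, part A) |

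One quantity, time since last dose, is undefined. Sex and depression score, the other covariates named in part C, are unaffected. The plan gives no coding for non-users, no current-use indicator and no rule for missing covariates.

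**Step 5. What would a coding rule do?** Let U = 1 for a current user and 0 otherwise, with dose D and duration L. In a model containing b1·U + b2·D + b3·L, setting D = L = 0 when U = 0 makes all three terms zero for non-users. They stay in the fit, b2 and b3 are estimated from users, and b1 takes up the difference between the groups. The same device does not give time since last dose a meaning for someone who takes none, so that analysis belongs among users.

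**The case against.** The best case for the plan has three parts.

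*The forms may differ.* The plan never equates the Opiate Pain inventory with the questionnaires in SubAim 1, and a non-user could answer a question about opiates. This stands as a caveat. But if there is a separate form, the protocol analyses an instrument that it never describes, and the text still needs repair.

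*No aim tests opiate reliance.* The hypotheses under Aims 1 and 2 concern the brain's response to pain, and the expected questionnaire results concern pain, discomfort, control and mood. That is correct, and it limits the harm. It does not remove it, because part B says that these four variables test the hypotheses of the Aims and supply effect sizes for the R01, and the Exploratory Analysis paragraph takes up craving measures again.

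*The covariate analyses are exploratory or optional.* This stands. A reader might infer that the planned covariate models will discard every non-user, and might turn that into lost sample size or power. The documents do not support that. They state no complete-case rule and list no opiate covariate in the time-by-treatment models. They do not give the share of users. Some participants will have no MRI, so the number in the imaging analysis is unknown too. The effect sizes under Sample Size come from healthy volunteers before and after a single session, which is not a treatment contrast in an exploratory covariate model. No power figure is offered here for those reasons.

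**Conclusion.** The outcome mismatch is wrong as written. Two of the four part B outcomes are named for opiates, while the only matching items described ask about any pain reliever, in a sample that includes non-users by design. Following the text would report general analgesic demand as opiate craving. This rests on one assumption, that part B analyses the SubAim 1 items.

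The covariate statement also contradicts the eligibility criteria, but its reach is smaller. A default complete-case fit could drop non-users from the exploratory time-since-dose analysis. How many cannot be said from the documents, and the main time-by-treatment models are not shown to lose anyone.

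**What to change.** 1. In Outcome Measure(s), part B, rename the two outcomes as collected (urge to use, and willingness to pay for, a pain reliever), and give the instrument the name used in General Methods. State that no conclusion about opiate craving or reliance will be drawn from them. If the inventory is in fact a separate form, describe its items and schedule instead.
2. In part C, correct the sentence that has every participant on a daily opiate dose.
3. Restrict the exploratory analysis of time since last dose to current opiate users.
4. In the other covariate models, keep non-users by adding a yes/no indicator of current use and setting dose and duration to 0 for them. This adds a parameter to a small exploratory model, so the choice should be fixed before the data are analysed.

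The cost is protocol wording. Dose and timing are already to be collected at each visit, and the questionnaire need not change. A claim about opiate craving itself would need an item that names opiates, which the protocol does not describe and this fix does not require.

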**Expected (and alternative) Outcomes:**

- A. **Quantitative Pain Testing.** Based on our pilot data, we expect an interaction between treatment (Real DPFC or MC TMS vs. Sham) and time (Before vs. After rTMS) on the painfulness QST measure but no effect on sensory or tolerance levels. Alternative outcomes: It is possible that individuals will experience a small level of acute pain relief from their normal regimen of medication. We will be collecting information on opiate dose and timing at each visit to be used as potential covariates. Further, there is the possibility that pain tolerance will rise, possibly also reflecting improvements in executive function.
- B. **Qualitative Pain Assessment.** We expect reductions in pain and discomfort when comparing active vs sham. However, based on prior data in opiate dependent individuals, we expect the effect size of DPFC rTMS in to improve measures of Control but not measures of mood, whereas MC will have a larger effect on mood.
- C. **Neuroimaging.** At baseline we expect that there will be elevated activations in the Pain Network in individuals with chronic pain. Following sham stimulation, we do not anticipate a significant reduction of this response. Based on prior studies by our group in non-opiate dependent individuals, following LTP-like stimulation of the DPFC, we expect a significant amplification of the DPFC (% BOLD signal change), and a reduction of the Pain Network (dACC, anterior insula) reflecting the increased influence of executive processes.

Alternative outcomes: Though pilot data suggest that a single treatment will acutely reduce self-reported pain, it is possible that the neural circuits in opiate dependent individuals do not have the same ‘plasticity potential’ as in controls. If we fail to replicate prior work showing DPFC activation, this could reflect executive deficits (58), suggesting that the MC TMS will be more efficacious.

**Exploratory Analysis:** We will evaluate if there are rate-dependent effects between baseline SN connectivity with the ECN and DMN and the efficacy of each TMS strategy on subjective pain. Data will be analyzed by using multivariate pattern analysis (MVPA) (2014). While the primary outcomes will be MRI V1 vs V2, we will also examine the relative ‘durability’ of the effects on pain by comparing the MRI data at the 1 month follow up between and within groups with factor analysis. **Integration of Brain based and Behavioral Based Outcomes with Gender and other Demographic Variables:** Finally, we will compare the relative efficacy of these two types of TMS using the behavioral and neuroimaging measures. Specifically, we will determine the effect sizes for DPFC and MC (relative to sham) stimulation on reducing the 1) the neural and 2) behavioral responses to pain, as well as 3) changes in clinical assessment metrics (see Approach). We will investigate the role of baseline cortical responsiveness on the pain response, as well as how changes in that evoked response are related to changes in both pain and craving measures. This will be specifically addressed as a factor of gender as

well, given that there are established differences in sensitivity to pain and prevalence of opiate dependence between men and women.

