The relative efficacy of these strategies will directly translate to development of a large clinical trial investigating rTMS as an innovative, new treatment option for pain in patients with CLBP.

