**SubAim 2: Evaluating Pain using Neuroimaging Data** At baseline we expect that people with chronic pain will have elevated activations in the Pain Network. This will be analyzed through the resting state connectivity network. Following sham stimulation, we do not anticipate a significant reduction of this response. Based on prior studies by our group in non-opiate dependent individuals, following LTP-like stimulation of the DPFC, we expect a significant amplification of the DPFC (% BOLD signal change), and a reduction of the Pain Network (dACC, anterior insula) reflecting the increased influence of executive processes. MC TMS however will likely not have as large of an effect on ECN engagement during the instruction to Control the pain.

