### **Analytical Plan**

See Outcomes Measures for the main plan of analysis.

Results will be analyzed initially using descriptive statistics. Comparison between groups will be done using chi square tests for proportions, and t-tests or ANOVA procedures for continuous variables. Regression analysis will be performed to identify independent outcome predictors. Other inferential statistical analysis will be conducted as appropriate.

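### The plan promises to compare DPFC with MC but specifies only separate effects against sham, so the DPFC-MC difference comes with no standard error or interval

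*Combined protocol and SAP*

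**What the plan says.** All references are to the combined protocol and SAP.

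- **Intent.** The Exploratory Analysis paragraph, under Expected (and alternative) Outcomes, states: "we will compare the relative efficacy of these two types of TMS using the behavioral and neuroimaging measures".
- **Method.** The next sentence makes this specific: "we will determine the effect sizes for DPFC and MC (relative to sham) stimulation on reducing" neural and behavioural responses to pain, together with changes in the clinical assessments. That is one sham-referenced effect per site.
- **Use.** Objectives closes with: "The relative efficacy of these strategies will directly translate to development of a large clinical trial".
- **Main model.** Outcome Measure(s), items A and B, sets up a time-by-treatment repeated-measures analysis in which "Real or Placebo TMS is the grouping variable". Two levels do not separate the sites. Expected Outcomes, item A, likewise expects an interaction of real stimulation at either site versus sham with time.
- **General methods.** Analytical Plan says: "Comparison between groups will be done using chi square tests for proportions, and t-tests or ANOVA procedures for continuous variables". No pairwise contrast is named.
- **Predicted site differences.** SubAim 2 (General Methods) says: "MC TMS however will likely not have as large of an effect on ECN engagement during the instruction to Control the pain". Expected Outcomes, item B, says of the questionnaires: "whereas MC will have a larger effect on mood". The alternative outcomes for neuroimaging add that failure to replicate DPFC activation could reflect executive deficits, and would suggest that MC is the more efficacious target.
- **Sample size.** The power statement concerns a pain-versus-rest fMRI effect. It does not address DPFC against MC.

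**The concern.** Two effects measured against the same sham arm, or one significant and one not, are not a test of the difference between them. Yet the plan makes several predictions that are differences between sites, and one passage treats a null at DPFC as evidence in favour of MC. A difference in significance against sham can easily arise when the sites are equally effective.

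What is at stake is interpretation. The plan says relative efficacy will inform the next trial, but as specified the reader of the results would get two estimates and no measure of how far apart they must be before the gap means anything. The comparisons of each site with sham are not affected.

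**Working it through.** **Inputs.** Arms of 16 DPFC, 16 MC and 16 sham; two-sided 0.05; effect sizes from 0.70 to 1.08 (all from Sample Size). Assumed: normal outcomes with equal SD in all arms, and effects in units of that SD. The plan's effect sizes come from a before-after study of 18 healthy controls, so applying them between arms is itself an assumption; results are therefore shown over a range.

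**The plan's own figure.** Sample Size states that n = 15 gives 80% power. A two-sample t-test with 15 per arm has 81.5% power at 1.08, and a paired t-test with n = 15 has 80% at 0.78, so the figure reproduces within the stated range. At 0.70 it does not: power is 71% paired and 46% two-sample. None of these calculations is about DPFC against MC.

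**Step 1: what the stated method yields.** With a single sham arm,

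(DPFC − sham) − (MC − sham) = DPFC − MC.

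The sham mean cancels. On the raw scale the point estimate of the site difference is already available.

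**Step 2: its precision.** SE = √(1/16 + 1/16) = √0.125 = 0.354 SD. With the variance pooled over three arms (45 df, t = 2.014), the 95% half-width is 2.014 × 0.354 = 0.71 SD. Using only the two active arms (30 df) it is 0.72.

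**Step 3: power of the direct contrast.** At 16 against 16, power is 13% for a true gap of 0.3 SD, 28% for 0.5 and 48% for 0.7. A gap of 1.02 SD is needed for 80%.

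**Step 4: equal sites, read through sham.** Three-arm trials were simulated with the same true effect at both sites, a shared sham and a two-sided t-test of each site against sham:

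| True effect at both sites (SD) | Exactly one site significant |
|---|---|
| 0.5 | 28% |
| 0.7 | 33% |
| 1.0 | 24% |
| 1.08 | 19% |

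As a check at 0.7: each test has power 0.483 and both are significant in 0.316 of trials, so exactly one is significant in 2 × (0.483 − 0.316) = 0.33. In the same trials the direct DPFC-MC test rejects in 5%. Among the trials with exactly one significant site, it rejects in about 12%.

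**Step 5: fewer completers.** Sample Size says some participants will have no MRI. If 12 per arm had data (an assumption), the SE is √(2/12) = 0.408 SD and the pooled half-width 0.83 SD.

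**The case against.** The best case for the plan has four parts.

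- This is a pilot meant to produce effect sizes, and the comparison sits under an exploratory heading. That stands. It argues for an estimate with an interval rather than a confirmatory test, and it limits how serious the point is.
- The intent to compare the sites is stated, and the ANOVA wording could accommodate a pairwise contrast. That also stands: a contrast is not ruled out, only not specified. But the sentence that makes the comparison specific points to sham-referenced effects.
- The stated method already gives the raw site difference. This is correct and narrows the point to the missing uncertainty.
- The plan speaks of effect sizes and nowhere proposes comparing p-values. So the 33% describes a misreading that the plan leaves open, not a procedure it sets out. The passage that moves from a DPFC null to MC being better shows that the misreading is not far-fetched.

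A reader might infer more: that the plan will pick the site with the larger estimate and carry it into the next trial. The documents contain no selection rule; they say only that relative efficacy will inform that trial's development. Nor would the contrast change which site has the larger estimate; it would show how uncertain the ordering is. A reader might also infer, from the split of sham between sites, that each site will be compared with its own sham participants. The plan describes one sham arm and no such comparison.

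**Conclusion.** The point holds as a gap in specification. The plan sets out to compare DPFC with MC and gives no standard error, interval or test for that difference. At 16 per arm the difference has an SE of 0.354 SD and a 95% half-width of about 0.71 SD, as large as the low end of the plan's assumed effect (0.70). With equal true effects of 0.5 to 1.0 SD, between 24% and 33% of trials would show exactly one site significant against sham. These figures rest on equal SDs, normal outcomes and complete data in 16 per arm; with fewer completers the interval is wider.

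The documents do not support saying that the plan omits any comparison of the sites, or that chance will decide which site goes forward.

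**What to change.** 1. In Outcome Measure(s) and Analytical Plan, make group a three-level factor (DPFC, MC, sham) in the group-by-time model.
2. Report the DPFC minus MC by time contrast with a 95% interval, labelled exploratory, for the behavioural, clinical and resting-state outcomes actually collected. The prediction about the instruction to control pain is outside this list, because the MRI session as described contains only an anatomical and a resting-state scan.
3. State that any claim that one site does better rests on that estimate and interval, and not on one site being significant against sham while the other is not. Reword the alternative-outcomes passage on a DPFC null to match.

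**Cost.** No additional participants, visits or procedures. It is somewhat more than adding a contrast to the existing model, because the two-level grouping variable must be redefined. The downside is that the site comparison will be seen to be imprecise.
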